4.1 Primary and secondary endpoints evaluated in the study

Primary endpoints evaluated in the study will be efficacy and safety parameters after single administration of the test drug or the placebo.

Primary endpoint: achieving clinical efficacy determined as:

Frequency of reducing number of adhesions after repeated MRI by 3 or more (in female patients with 10 and less adhesions at the baseline) or by 30% and more (in patients with >10 adhesions at the baseline)) in comparison to baseline MRI data

Secondary efficacy endpoints:

1. Change in thickness of pelvic adhesions by repeated MRI in comparison to baseline MRI data
2. Frequency of limited displaceability of pelvic organs in post-surgical period (based on results of transvaginal ultrasound investigation) on Day 30±4 after the surgery
3. Frequency of hyperechoic linear lesions in post-surgical period based on results of transvaginal ultrasound investigation
4. Change in frequency of detecting limited displaceability in comparison to baseline (absolute change and in % of baseline value)
5. Changes in frequency of detecting hyperechoic linear lesions based on repeated transvaginal ultrasound investigation in comparison to baseline
6. Frequency of detecting complete absence of USI – signs of adhesion process in the pelvis in post-surgical period (defined as absence of limited displaceability of pelvic organs and absence of hyperechoic linear lesions)

Safety parameters:

- Vital signs (body temperature, BP, HR, RR)
- Laboratory parameters:

Blood chemistry – total protein, glucose, ALT, AST, total bilirubin, alkaline phosphatase, amylase, creatinine

Complete blood count – RBC count, WBC count, platelet count, hemoglobin, hematocrit, WBC differential, ESR

Coagulogram – coagulation time, international normalized ratio (INR), thrombin time, activated partial thromboplastin time (APTT)

Urinalysis – color, transparency, pH, specific gravity, protein, glucose, WBC, RBC, bacteria, casts, salts

- ECG data – heart rate [HR], PR, QRS, QT intervals and calculated QTc interval.
- USI data

- Incidence of adverse reactions
- Incidence of serious adverse reactions
- Incidence of unexpected adverse reactions
- Incidence of adverse and serious adverse reactions caused termination/withdrawal from the study.

4.2 Description of the study design, graphical scheme of the study design, procedures and stages of the study

4.2.1 Description of the study design

A multicenter randomized double-blind placebo-controlled clinical study of efficacy and selection of dose of the drug Seroguard, solution (JSC Pharmasyntez, Russia) used for prevention of pelvic adhesions will be performed.

After successful completion of screening procedures, a female patient will undergo a planned laparoscopic surgery. Randomization of female patients into groups will be performed on the day of surgery using an online IWRS system (Interactive Web Response System). The test drug or the placebo are used at the final stage of the surgery. A female patient is planned to be under control in the hospital for 6 days after completion of the surgery. On Day 7 of the study, a female patient may be discharged from the hospital, if there are no any contraindications, in this case a follow-up of a female patient is performed on outpatient basis. Follow-up lasts for 4 weeks, up to Day 28 of the study. Then a complete evaluation of treatment efficacy after repeated MRI-investigation of the abdominal cavity and the pelvis is performed.

Study procedures aimed at evaluating safety and efficacy of the test drug and the placebo will be identical in all the groups:

- 1) Placebo group, 1.5 mL/kg – up to 30 screened female patients which corresponds to 26 randomizations and 24 completed cases
- 2) Placebo group, 2.4 mL/kg – up to 30 screened female patients which corresponds to 26 randomizations and 24 completed cases
- 3) Seroguard group, 1.5 mL/kg – up to 30 screened female patients which corresponds to 26 randomizations and 24 completed cases
- 4) Seroguard group, 2.4 mL/kg – up to 30 screened female patients which corresponds to 26 randomizations and 24 completed cases

4.2.2 Graphical scheme of the study design

[figure not shown]

Figure 2 – Graphical scheme of the study

4.2.3 Description of the study procedures

Table 1 – Schedule of the study procedures

Procedures	Screening	Surgery	Follow-up		Unscheduled visit ¹	Withdrawal visit
	Visit 0	Visit 1	Visit 2	Visit 3		
	Day from -15 to -1	Day 0	Day 6±1	Day 30±4		
Informed consent	+					
Evaluation of inclusion, non-inclusion criteria	+	+				
Evaluation of withdrawal criteria			+		+	
Collection of medical and pharmacotherapeutic analysis	+					
Collection of demographic and anthropometric data	+					
Physical examination	+	+	+	+	+	+
Evaluation of local status		+	+	+	+	+ ²
Measurement of vital signs ³	+	+	+	+	+	+
HIV, RW, HBV and HCV blood test	+					
Pregnancy test	+			+		+
Randomization		+				
Complete blood count	+		+	+	+	+
Blood chemistry	+		+	+	+	+
Coagulogram	+			+		+
Urinalysis	+		+	+	+	+
MRI of abdominal cavity and pelvic organs	+			+		+
USI of abdominal cavity	+		+			+
USI of pelvic organs	+			+		+
Gynecological examination and colposcopy	+					
Cytological examination (Pap-smears)	+					
Smear microscopy	+					
Hysterosalpingography ⁴	+					
12-lead ECG	+		+	+	+	+
Evaluation of concomitant therapy		+	+	+	+	+
Administration of the test drug/placebo		+				
Detection of ARs	+	+	+	+	+	+

¹ Any additional study procedure may be performed in case of indications, at the discretion of the Principal Investigator.

² If applicable

³ Blood pressure, heart rate at the radial artery, respiration rate, body temperature will be measured.

⁴ Performed at the discretion of a doctor for women included into the study with diagnosis "infertility".

4.2.3.1 Collection of demographic data and history, anthropometry

During screening visit after signing informed consent, the following data will be collected from all the patients:

- Race, age (birth date).
- Body weight (kg), height (cm), BMI (kg/m²).
- Detailed medical history, including:
 - previous surgeries and traumas;
 - previous diseases
 - allergy history;
 - drugs used within the previous 30 days or 5 half-lives (which is longer) before visit of screening and used concomitantly, as well as herbal drugs and additives.
- Collection of gynecological anamnesis:
 - Beginning of menses and their nature;
 - Date of beginning of the last menses;
 - Presence/absence of previous pregnancies, their course and outcome;

Female patients signing informed consent should also provide consent to comply with efficient contraception throughout the study. Effective methods of contraception are use of one of the following methods (considering inclusion/non-inclusion criteria for the present study):

- Complete abstinence.
- Double barrier method: condom or occlusive cap (diaphragm or cervical/vault cap) plus spermicide (foam/gel/film/creme/suppository).

Women are obliged to comply with an adequate method of contraception throughout the whole study period.

4.2.3.2 Physical examination

Physical examination will be performed at all the visits in order to reveal normal or changed physical data of patients, that were before administration of the study drug, as well as to reveal possible changes during and after its use. Acceptable terms of investigation performance are specified in section 4.2.4.

Physical examination includes:

- general condition of female patient;
- condition of skin;
- musculoskeletal system;
- lymphatic nodes;
- thyroid;
- upper respiratory tract and lungs;
- heart, blood vessels;

- abdominal cavity organs, kidneys;
- psycho-neurological status.

4.2.3.3 Evaluation of vital signs

Evaluation of vital signs will be performed at each visit. Acceptable terms of performance are specified in section 4.2.4. Evaluation includes:

- measurement of axillary temperature;
- measurement of systolic and diastolic blood pressure (BP);
- count of heart rate per 1 minute;
- count of respiration rate (RR) per 1 minute.

Measurements are performed in seated or semirecumbent position after 5 minutes of rest on one and the same hand (for measurement of BP and heart rate) and, if possible, by one and the same specialist of a clinical site during participation of a particular female patient in the study.

4.2.3.4 Evaluation of local status (condition of postsurgical wounds)

To be evaluated:

- Palpatory tenderness
- Hyperemia
- Edema
- Presence of discharge

4.2.3.5 Laboratory investigations

Scheduled blood and urine tests will be performed at screening (after signing informed consent) (Visit 0) and during visits 2 and 3, as well as in case of unscheduled visit and withdrawal visit. The following laboratory parameters will be determined/evaluated for the given studies:

- Blood chemistry – total protein, glucose, ALT, AST, total bilirubin, alkaline phosphatase, amylase, creatinine.
- Complete blood count – RBC, WBC, platelet count, hemoglobin, hematocrit, WBC differential, ESR.
- Coagulogram – coagulation time, international normalized ratio (INR), thrombin time, activated partial thromboplastin time (APTT) – *performed only at visits 0, 3 and at withdrawal visit.*
- Complete urinalysis with sediment microscopy - color, transparency, pH, specific gravity, protein, glucose, WBC, RBC, bacteria, casts, salts.
- HIV, RW, HBV and HCV blood tests – *only at screening.*

Clinical laboratory investigations will be performed by local laboratory of a clinical site according to the standards of a respective site (including methods of biological sample collection and performance of laboratory investigations). Medical Investigator will obtain the study results,

review, evaluate clinical significance of each parameter deviation from normal values (used in the local laboratory), put date and signature and store as a primary documentation. Samples of blood and urine for laboratory investigations are taken in fasting conditions, i.e. within 10 hours before sampling, a female patient of the study should not eat and drink anything, except for water.

Pregnancy test will be performed at screening (Visit 0) and at Visit 3, as well as at withdrawal visit, in a clinical site using strip-test (lateral flow immunoassay of beta-chorionic gonadotropin in urine).

Cytological examination (Pap-smear) and microscopic (bacterioscopic examination) examination of smears stained by Gram's method. Smears for microscopy are taken from cervical canal, vagina and urinary tract. Smear is taken by spatula which does not injure mucosa of the specified organs and collect discharge in their lumen. Before collection of smears, gynecologist introduces a gynecological speculum into vagina. A material taken is applied on a glass slide and is sent to laboratory.

4.2.3.6 Instrumental studies

Electrocardiography

Acceptable terms of ECG performance are specified in section 4.2.4.

Standard 12-lead ECG (with measurement of heart rate [HR], PR, QRS, QT intervals and calculation of QTc) will be performed in prone position after 5 minutes of rest. Recording rhythm in the respective leads should contain evaluable data of at least three cardiac cycles. All the changes in ECG should be subjected to evaluation by a primary care physician.

If any changes in ECG, Medical Investigator should evaluate their clinical significance. If clinically significant deviations at screening, Medical Investigator should evaluate possibility of inclusion of patient into the present study, at Visit 2 and 3 or in case of unscheduled visit or withdrawal visit – to evaluate conformity to AR criteria (see section 8.2).

Ultrasound investigation of abdominal cavity and retroperitoneum

It is performed twice at Visits 0 and 2 as well as at withdrawal visit of the study as per the unique method presented in the separate guideline.

Performance of pelvic USI

Pelvic USI is performed at Visits 0 and 3 as well as at withdrawal visit of the study as per the unique method presented in the separate guideline, using transvaginal probe. Video recording of the performed investigation is required! Disc with the study results is attached to the primary documentation.

Performance of MRI of abdominal cavity and pelvis

The study is performed under fasting conditions (a female patient should starve before the investigation for at least 4 hours). 0.5 – 1.0 hours before the investigation, a female patient should

void the bladder and colon. Before the investigation, features of abdominal cavity and pelvic MRI performance will be explained to a female patient in detail.

MRI of the abdominal cavity and the pelvis is performed at Visits 0 and 3, as well as at withdrawal visit as per the protocol of MRI investigation which will be provided in a separate guideline along with evaluation of adhesion severity according to the following method defined by the Sponsor:

Prevalence in abdominal cavity:

1. absence of adhesions;
2. one floor (up to 3 segments of one level);
3. two floors;
4. total adhesive process.

Prevalence in pelvic cavity:

1. Absence;
2. One region (right lateral space, left lateral space, pouch of Douglas or vesicouterine pouch);
3. Two regions;
4. Subtotal adhesive process in the pelvis (3 regions);
5. Total adhesive process in the pelvis.

Maximum severity of adhesions:

1. Thin (filmy or filiform);
2. Severe;
3. Severe with impaired passage through organs involved into the process (narrowing of the intestines for more than ½ of the lumen or hydrosalpinx).

Score of assurance evaluation is given for every adhesion in its presence:

absolute assurance, that the adhesion is present – 4;

adhesion is, probably, present – 3;

adhesion is, possibly, present – 2;

difficult to determine whether adhesion is present or absent – 1.

Pelvic adhesion index is determined:

PAI (pelvic adhesions index) = (A+B)*Ccp,

Determine as per the Tables A and B:

A – Prevalence of pelvic adhesive process		B – Maximum severity of adhesions	
Absence	0	Absence	0

One region (right lateral space, left lateral space, pouch of Douglas or vesicouterine pouch)	1	Thin (filmy or filiform)	1
2 regions	2	Severe	2
Subtotal adhesive process in the pelvis (3 regions)	3	Severe with impaired passage through organs involved into the process	3
Total adhesive process in the pelvis	4		

Ccp value is an arithmetic mean of assurance evaluation score during description of each detected adhesion.

Record of MRI-investigation results in DICOM-format will be sent to the study Sponsor for centralized evaluation in independent laboratory. Meanwhile, information on female patient by whom it could be identified, including therapy group, will remain blinded.

Hysterosalpingography

Hysterosalpingography is performed at Visit 0 at the discretion of a doctor only for female patients included into the study with diagnosis of infertility. May not be performed in case of hysterosalpingography results obtained on Day 7-10 of menstrual cycle at least 6 months before visit 0.

Water-soluble contrast agents are most commonly used for hysterosalpingography (50, 70% solutions of Cardiotrast, 60, 76% solutions of Triombtrastum, 60, 70% solutions of Urotrast, 76% solution of Verografin, etc.). Performed using radiotransparent urological examination chair by digital radiography equipment which permits to decrease radiation dose for patient. She is put on the edge of a table in a position comfortable for vaginal procedures. After treatment of vulva with disinfectant, a bimanual pelvic examination is performed. Spoon-shaped vaginal speculum is introduced into vagina. Its walls are wiped by dry cotton ball, and then by cotton ball moistened with alcohol. Anterior lip of cervix uteri is caught by bullet forceps, without piercing cervical canal mucosa reach with receptors.

Schultz cannula consisting of a tube 30-35 cm length is used for hysterosalpingography. Its internal diameter is 1.5-2.0 mm. One end of tube is connected to 10 or 20-gramm syringe. A cone-shaped tip is fixed on the other end; it is introduced into cervical canal in order to close external orifice of the uterus. There is a “rider” with a screw on the tube, on which ends of bullet forceps are fixed so as to firmly retain the tip in the cervix. Cannula is filled with contrast agent heated up to the body temperature. After ensuring in tightly closed external orifice by introducing a small quantity of contrast agent into uterine cavity a speculum is removed, and the woman is placed on the table so as to permit a central roentgen ray to pass through the upper edge of the uterus. In order to protect a doctor from roentgen radiation along with X-ray protection apron, fixed on radiography equipment for urological investigations, a mobile lead screen protecting the body and legs of a doctor is used. 2-3 mL of contrast agent are used for obtaining a first image in order to get a uterine cavity three-dimensional image. After treatment and examination of the first image, 3-4 more mL of contrast agent are added and the second image is obtained. In this case tighter filling of uterine cavity is obtained, and the contrast agent gets into tubes and abdominal cavity. After examination

of a second image, a third image is obtained, if needed. 10-20 mL of contrast agent are usually used for the whole procedure. During hysterosalpingography using radiography equipment with electro-optical converter on a TV screen, gradual filling of uterine cavity and tubes, movement of contrast agent into abdominal cavity may be seen, images are made while filling uterine cavity and tubes. On the day of procedure, it is required to shave pubic hair, and if no stool, perform cleansing enema. Before the procedure, void the bladder. After the procedure, patients should have rest on a couch for 40-60 min.

Gynecological examination

Gynecological examination of vulva, vagina and cervix is performed at Visit 0 as per the medical-economical standard (the study using speculum and bimanual examination) with obligatory recording of the following parameters:

- color of vaginal and cervical mucosa;
- presence or absence of abnormal changes (scars, polyps, erosions);
- form of cervix (conical, cylindrical, deformed);
- form of exterior mouth of the uterus (round, slit-like);
- nature of discharge

Colposcopy

Colposcopy represents a diagnostic examination of vaginal orifice, vaginal walls and portio vaginalis using colposcope (lightening device and binocular with 40-fold magnification). Before the procedure, a woman should abstain from sex, vaginal douche, use of vaginal tablets and other topical drugs several days before the visit to a doctor. On the day of the procedure, a woman should wash her genitals with warm water and soap. There are not restrictions on the day of menstrual cycle.

Procedure of colposcopy is the following – after a careful introduction of speculum, examine cervix and remove mucus. When introducing speculum and wiping cervix with cotton wool ball, try not to traumatize mucosa, otherwise it will be impossible to evaluate epithelium changes correctly. After introduction, a colposcope is fixed at the distance of 20-25 cm from the surface examined. Beam of light is directed on the cervix and, looking through the colposcope, ocular lenses are fixed so as to obtain a clear image of mucosa vaginal part of cervix, vaginal walls or vulva. Cervix is examined clockwise or by zones.

Then, 3% acetic acid is applied on uterine cervix, under its effect, mucosa is removed, and epithelium cells become whitish-grey. Acetic acid solution starts to act 30-60 seconds after application of mucosa and lasts for 3-4 minutes. Then 2% Lugol's aqueous solution is applied, after that a healthy mature stratified squamous epithelium of uterine cervix is colored into dark-brown color (positive Shiller's test). All the abnormal sites of tissue after exposure of Lugol's solution are not colored or colored into slightly-yellowish.

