	
8. Laboratory parameters:
 
Blood chemistry – total protein, glucose, ALT, AST, total bilirubin, alkaline phosphatase, amylase, creatinine
 
Complete blood count – RBC count, WBC count, platelet count, hemoglobin, hematocrit, WBC differential, ESR
 
Coagulogram – coagulation time, international normalized ratio (INR), thrombin time, activated partial thromboplastin time (APTT)
 
Urinalysis – color, transparency, pH, specific gravity, protein, glucose, WBC, RBC, bacteria, casts, salts
 
9. ECG data – heart rate [HR], PR, QRS, QT intervals and calculated QTc interval.
 
10. USI data
 
11. Incidence of adverse reactions
 
12. Incidence of serious adverse reactions
 
13. Incidence of unexpected adverse reactions
 
14. Incidence of adverse and serious adverse reactions caused termination/withdrawal from the study

Study procedures
	
Visit 0 – Screening
 
 • Obtaining informed consent • Collection of history, demographic data • Gynecological history • Collection of previous therapy information • Physical examination with evaluation of vital signs • Laboratory investigation: complete blood count, blood chemistry, coagulogram, urinalysis, pregnancy test (performed not earlier than on the day 7 before surgical intervention), HIV, HBV, HCV and RW blood test • ECG • USI of the abdominal cavity • USI of the pelvic organs (transvaginal) (in the second phase of the menstrual cycle) • MRI of the abdominal cavity and the pelvic organs

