	
• Gynecological examination and colposcopy• Cytological examination (Pap-smears)• Microscopic (bacterioscopic examination) examination of the smear stained by Gram's method• Assessment of the inclusion/non-inclusion criteria compliance• Only for female patients included into the study with diagnosis "infertility" - hysterosalpingography (Day 7-10 of the menstrual cycle), use of hysterosalpingography results obtained on Day 7-10 of the menstrual cycle within 6 months before screening visit is permissible 
Visit 1 (Day 0)
 
Before the surgery:
 
• Physical examination with evaluation of vital signs• Actualization of the information on concomitant therapy• Actualization of the information on concomitant disease• Reassessment of inclusion/non-inclusion criteria• Randomization• Surgical intervention using the test drug or the placebo• Evaluating severity of baseline adhesion process (intraoperative) 
After the surgery:
 
• Physical examination with evaluation of vital signs• Local status assessment (description of postsurgical wound)• Adverse reaction assessment 
Visit 2 Interim safety assessment (Day 6±1)
 
• Physical examination with evaluation of vital signs• Laboratory investigations: complete blood count, blood chemistry, urinalysis• Local status assessment (description of postsurgical wound)• USI of the abdominal cavity• ECG
--	--

	
 • Adverse reaction assessment 
Visit 3 (30±4 days after the surgery)
 
 • Physical examination with evaluation of vital signs. • Local status assessment (description of postsurgical wound) • Adverse reaction assessment • Laboratory investigations: complete blood count, blood chemistry, coagulogram, urinalysis, pregnancy test • ECG • USI of the pelvic organs (transvaginal) with the adhesion severity evaluation • USI of the abdominal cavity • MRI of the abdominal cavity and the pelvis

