2.3 Known and potential risks and benefit for the study subjects

2.3.1 Risks and inconveniences related to participation in the study

ARs related to administration of the test drug and characteristic for the group of p38 MAPK inhibitors may be observed as well as AR not previously noted (known ARs during treatment with p38 MAPK inhibitors are provided in section 2.2.2.) may be noted during this study. Safety profile of p38 MAPK inhibitors is satisfactory even during systemic use, and considering the absence of Seroguard absorption from the abdominal cavity according to pre-clinical data, it is possible to calculate good tolerability of the drug. Based on results of the Phase I clinical study, safety profile of the drug Seroguard was comparable to that of placebo. Thus, AR incidence in the group of treatment with the test drug is expected not to exceed the similar parameter in the placebo-control group (risk related to the underlying disease which is an indication for surgery, risk of surgery and anesthesia).

Blood sampling for clinical laboratory investigations (see section 4.2.3.5) may be accompanied by mild pain which is fleeting and/or ecchymoses may be formed at the site of needle injection. A thrombus may be formed in vein or infectious complication may be developed significantly rarer. Dizziness and/or fatigue may be observed during and soon after blood sampling.

Electrocardiographic examination (see section 4.2.3.6) is a painless examination, however rash or irritation may develop on patient's skin at the sites of gel application and using sticky electrodes for ECG.

Ultrasound investigation (see section 4.2.3.6) – In the present study, USI of the abdominal cavity is performed by transabdominal access and USI of the pelvis - by transvaginal access. The latter may be accompanied by mild painful sensations.

Hysterosalpingography. Rare complications of performing HSG include development of acute or chronic endometritis (in cases when bacteria along with contrast agent get from vagina into the uterine cavity), as well as allergy to contrast agent (contrast contains iodine, that's why presence of allergy to iodine should be specified in all women before HSG). Exceedingly rare complication of HSG is injury of fallopian tubes and/or uterine. In addition, during HSG a woman receives a small dose of X-ray irradiation (control of maximum individual effective irradiation dose is required).

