4.2.4 Description of periods and visits of the study

4.2.4.1 Screening period

Visit 0 (from Day -15 to -1 of the study)

The following will be performed at the visit:

- Obtaining informed consent (see section 12.2). All the screening procedures will be performed only after obtaining informed consent.
- Collection of history, demographic and anthropometric data, gynecologic history (see section 4.2.3.1).
- Collection of information on previous therapy (see section 4.2.3.1).
- Physical examination (see section 4.2.3.2).
- Evaluation of vital signs (see section 4.2.3.3).
- Laboratory investigations: complete blood count, blood chemistry, urinalysis, coagulogram, pregnancy test, HIV, HBV, HCV and RW blood test (see section 4.2.3.5).
- ECG (see section 4.2.3.6).
- USI of the abdominal cavity, pelvis (see section 4.2.3.6).
- MRI of the abdominal cavity and the pelvis (see section 4.2.3.6).
- Gynecological examination and colposcopy (see section 4.2.3.6).
- Cytological examination (PAP-smears) (see section 4.2.3.5).
- Microscopic (bacterioscopic examination) examination of the smear stained by Gram's method (see section 4.2.3.5).
- Hysterosalpingography (see section 4.2.3.6).
- Evaluation of inclusion/non-inclusion criteria compliance (see section 5).
- Evaluation of AR (see section 8).

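### Section 4.2.3.6 reverses the age limit for reusing an earlier hysterosalpingography film: it waives the procedure for films at least 6 months old, where the Synopsis accepts films no more than 6 months old

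*Protocol*

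**What the plan says.** The rule on earlier hysterosalpingography films appears in two places.

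- **Synopsis, Study procedures, Visit 0.** The procedure is listed only for women included with a diagnosis of infertility, and reuse of an earlier film is allowed: "use of hysterosalpingography results obtained on Day 7-10 of the menstrual cycle within 6 months before screening visit is permissible".
- **Section 4.2.3.6, Hysterosalpingography.** The procedure is discretionary: "Hysterosalpingography is performed at Visit 0 at the discretion of a doctor only for female patients included into the study with diagnosis of infertility". The next sentence gives the waiver: "May not be performed in case of hysterosalpingography results obtained on Day 7-10 of menstrual cycle at least 6 months before visit 0".

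Three other places bear on how these are read.

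- **Section 4.2.4.1** lists the procedure at screening and refers the site to the body text: "Hysterosalpingography (see section 4.2.3.6").
- **Table 1, footnote 4** (section 4.2.3) repeats the discretion and gives no film age: "Performed at the discretion of a doctor for women included into the study with diagnosis" of infertility.
- **Section 2.3.1** describes the risks: "Rare complications of performing HSG include development of acute or chronic endometritis". It also names contrast allergy and, as exceedingly rare, injury to the tubes or uterus. It describes the X-ray dose as small but adds that "control of maximum individual effective irradiation dose is required".

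**The concern.** A rule for reusing an earlier image normally limits its age: a recent film can stand in and an old one cannot. The Synopsis does this. Section 4.2.3.6 sets a minimum age instead of a maximum, with no upper limit. It gives a written waiver to every old film and none to a recent one.

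Two things could follow at a site working from 4.2.3.6. A woman with a recent film that the Synopsis would accept could be examined again. Or a film of any age above 6 months could be taken as sufficient, which the Synopsis does not allow.

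The first matters more to the patient. As 4.2.3.6 describes it, the examination involves forceps on the cervix, contrast passed through the uterus and tubes into the abdominal cavity, and two X-ray images, with a third if needed.

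**Working it through.** No sample size, power or error rate depends on this sentence and the plan gives no figure to reproduce, so the check is a comparison of the two rules.

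**Common anchor.** The Synopsis counts back from the screening visit and section 4.2.3.6 from Visit 0. The Synopsis labels the visit "Visit 0 – Screening", so these are the same point in time. Both rules also require a film from cycle Day 7-10. They differ only in the direction of the 6-month limit.

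**The two windows.** Let t be the age of the film in months at Visit 0.

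- Synopsis: film accepted if 0 ≤ t ≤ 6.
- Section 4.2.3.6: waiver applies if t ≥ 6, with no upper bound.
- Overlap: t = 6 only.

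| Film age at Visit 0 | Synopsis | Written waiver in 4.2.3.6 |
|---|---|---|
| 2 months | accepted | does not apply |
| exactly 6 months | accepted | applies |
| 24 months | not accepted | applies |

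**Two readings of the verb.** The waiver's opening words can mean that the procedure need not be done or that it must not be done.

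- *Need not.* Old films are excused whatever their age, and recent films get no written excuse.
- *Must not.* A new examination is barred in a woman whose film is 6 months old or older, although the Synopsis would not let that film stand in. A woman with a recent film has no such protection.

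The window is reversed on either reading, so the ambiguity does not resolve the conflict.

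**Search for a tie-breaker.** Section 4.2.4.1 points to 4.2.3.6, the reversed text. Table 1 footnote 4 gives no window. No statement in the Protocol says whether the Synopsis or the body prevails. Both sentences are complete, so this is not a gap left by redaction or PDF extraction.

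**Who can be affected.** The Protocol plans to screen 120 women. Only those with a diagnosis of infertility and an earlier Day 7-10 film are exposed to the conflict, and neither number is given. The introductory text before section 2.1 describes adhesiolysis for tubo-peritoneal infertility, so the group may not be small, but 120 is only an outer bound.

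**The case against.** The case for treating this as trivial has four parts.

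1. **Discretion.** Section 4.2.3.6 and Table 1 footnote 4 leave the procedure to the doctor. A doctor may omit it with no film at all, so accepting an old film is no looser than what is already allowed. A repeat of a recent film would need a doctor to choose it despite the Synopsis permission and the dose-control statement in 2.3.1.
2. **No role in the trial's results.** The inclusion criteria rest on gynecological examination and ultrasound. Hysterosalpingography is named in neither the inclusion nor the non-inclusion criteria, and it is not an endpoint or an analysis variable.
3. **Obvious intent.** The slip looks like a translation error, and most readers would guess that the Synopsis is right.
4. **No numbers.** The affected group cannot be sized.

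The second and fourth parts stand in full and limit the importance of the point. The first stands in part: nobody is obliged to repeat a recent film, and the harm from an accepted old film is slight. But discretion appears only in the body and the table. The Synopsis lists the procedure for infertility patients without it, and so does 4.2.4.1. Monitoring under section 11.1 includes checking that sites follow the Protocol's diagnostic procedures, and a monitor would get opposite answers from the two texts. The third part is a plausible inference about cause, but the source-language text is not available, and a site should not have to guess which of two contrary instructions applies to an X-ray procedure.

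**Conclusion.** The point holds. The Synopsis and section 4.2.3.6 give opposite age limits for a reusable film, counted from the same visit, and agree only at exactly 6 months. The body wording is almost certainly the wrong one, because a recency limit is the sensible rule for reusing an image; that is a judgement, since the Protocol does not say which text governs.

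The size is modest. It concerns an unneeded repeat of an invasive contrast and X-ray examination, or reliance on an outdated film, in an unstated number of infertility patients among the 120 to be screened. No randomization decision under the written criteria, efficacy or safety endpoint, or analysis is affected. It should be corrected because it is a patient-facing instruction that is wrong as written, even though the trial's inference does not depend on it.

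**What to change.** In section 4.2.3.6, replace the minimum film age with a maximum: a new hysterosalpingography need not be performed if results from cycle Day 7-10, obtained within 6 months before Visit 0, are available. Writing *need not* also removes the ambiguity of the verb. Optionally, refer Table 1 footnote 4 to that rule. The same edit could settle whether the procedure is discretionary, as in 4.2.3.6 and Table 1, or standard for infertility patients, as the Synopsis implies.

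The cost is one corrected phrase and, if wanted, one cross-reference. No procedure, visit or patient is added.
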